## Part B

Framework thematic analysis (Illiffe et al 2015) will be used to analyse the qualitative data using NVivo software. The 5 key stages of framework analysis will be used as follows:

1. Familiarisation: data will be sensitised into early themes, individual difference within and between transcripts will be identified
2. Identifying a thematic framework: key themes, issues and discussion points will be identified and given a code/ label
3. Indexing: transcripts will be annotated numerically in order to identify a consistent coding framework
4. Charting: the final coding framework will be synthesised and developed
5. Mapping and interpreting: the main themes identified from the data will be represented pictorially/ graphically to demonstrate how they interact with and relate to each other

## 12. Patient and public involvement

---

This research proposal was presented to the Patient and Carers Research Review Panel at the Royal Marsden Hospital on 16.1.2019. This group included two HNC patients, one of whom has recurrent disease, carers and lay volunteers. The NIHR Research Design Service (RDS) Enabling Involvement Fund was also awarded to the research team to further involve patients and carers in the design of this study. Using this initial funding a small group of patients who have undergone treatment for recurrent OPC were invited as a PPI research steering group specific to this project. A meeting with this group was held on 22.2.2019. Two of the patients attended and a further four provided feedback and advice remotely. The research proposal was presented for discussion. This research has also been discussed with [name], Chair of the Swallows Head and Neck Cancer Charity. Opinions were sought on the research idea/question and the data collection methods including interviews and proposed functional outcome measures.

The PPI groups explained the following:

- The research question was '*important*' and '*worthwhile*' and commented on the importance of capturing information about functional outcomes '*I would have found information on*

*speech and swallowing very helpful in my decision making...I didn't have that information and that was what I was worried about'*

- It was crucial to use interviews in addition to functional outcome measures, as 'not all information can be captured by clinical tools'
- Carers should be included as interviewees, as key functional concerns and QoL concerns will impact carers too. They explained that communication and eating and drinking '*is social*' involving '*more than just the patient*' and that '*patients and families "hear" different things*', '*the diagnosis, treatment and aftermath have such an impact on the family as a whole*'.
- The outcome measures outlined in the research proposal were '*acceptable*', including objective measures which are sometimes '*reassuring*'; '*I seem to be able to tolerate nasendoscopy fairly well and find it helpful and reassuring to know what is going on with my swallow*'.

### 13. Study organisation/ Trial Monitoring and Management Strategy

---

### **Data quality checks**

Part A: One of the co-investigators who is not involved in the data collection will check the accuracy of 10% of all of the anonymised data entered into the excel spreadsheet.

Part B: One of the co-investigators will review 10% of the anonymised interview transcripts to verify coding process.

### **Timeline**

The protocol will be submitted for scientific review by the Committee for Clinical Research and for local management R&D approval and REC. The PI/CI will be notified in writing of the CCR/ R&D Approval. The study will then be activated on the Hospital Information System and the PI/CI will be notified that the study is open for recruitment. This date will be classified as start date for the R&D database.

The data collection period will continue for 18 months or until 44 patients have been recruited and longitudinal data obtained and 15-20 patients and 12-15 carers have taken part in 2 interviews at baseline and 6 months.

## **14. Safety reporting**

---

This is a non-invasive study involving routine clinical assessments of function and validated questionnaires designed to identify the presence and symptoms of dysphagia/ communication difficulties and the impact on QoL. Due to the non-interventional nature of the study, adverse events will not be recorded.

The participant may present with a dysphagia. If dysphagia is identified, referral for SLT assessment will be made and the medical team and G.P. informed. Other issues may also arise such as compromised nutritional status or psychological distress. If such issues arise appropriate referrals will be initiated following liaison with the medical team i.e. Dietitian referral, Psychological Support etc.

Participation in interviews/ questionnaires may cause potential upset or emotional distress. The participant's cancer key worker (Head and Neck CNS) will be aware of the patient's participation and will be available to provide psychological support in the event that the participant becomes upset.

## **15. Regulatory & Ethics Committee Approval**

---

The study will be reviewed by the Committee for Clinical Research (CCR) and the Health Research Authority (HRA). HRA approval conditions will be followed.

## 16. Data handling and record keeping

---

All data will be handled in accordance with the UK General Data Protection Regulation (UK GDPR) and the Data Protection Act 2018. The CRFs will not bear the participant's name or other directly identifiable data. The participant's study Identification Number (PIN) only, will be used for identification. The Subject PIN log will be used to cross reference participant's identifiable information. All data from the paper CRFs and questionnaires will be collected in an excel spreadsheet using PINs only.

The ISF and excel spreadsheet, will be stored at the Royal Marsden NHS Foundation Trust. All data will be coded and no identifiable reference to the participants will be held with the data. Paper CRFs and questionnaires and interview transcripts will be stored in locked, fireproof file cabinets. Coded data held electronically will be stored on password protected NHS computers. In the event of remote working, the secured RM sharedrive can be accessed and used by members of the research team employed by the Royal Marsden. Anonymised audio interview data will be transferred securely to an external transcription service.

The investigator site file will include ICFs, questionnaire response forms, and CRFs. The questionnaire responses and CRFs will not bear identifiable information as the anonymous study identification (PIN) number will be used. The ICFs will be stored securely separate to the anonymised data in a locked fire proof filing cabinet held in the SLT department at the Royal Marsden Hospital.

The Royal Marsden NHS Foundation Trust will permit study-related monitoring, audits, REC review, and regulatory inspection(s), providing direct access to source data/documents. Participants are informed of this during the informed consent discussion. Participants will consent to provide access to their medical notes

## 17. Financing, Indemnity & Insurance

---

This study will form part of a PhD training fellowship, being undertaken at Imperial College London by a student who is employed by the Royal Marsden NHS Foundation Trust, as Clinical Lead Speech and Language Therapist. The Clinical Doctoral Research Fellowship has been funded by the National Institute of Health Research. The study is supported by The Royal Marsden NHS Foundation Trust. Where the Royal Marsden NHS Foundation Trust is either sponsoring or collaborating with externally sponsored research the NHS Litigation Authority will cover standard clinical negligence by employees, staff and health professionals employed by the Royal Marsden NHS Foundation Trust.

For more information visit the following website:

<http://www.nhsla.com/Claims/Pages/Clinical.aspx>

There is unlimited liability and no excess. Insurance is provided under the Clinical Negligence Scheme for Trusts and there is no cover for non-negligence claims.

## 18. Publication policy

---

The PI is responsible for approving the content and distribution of all publications, abstracts and presentations arising from the study and for assuring the confidentiality and integrity of the study. The data arising from the project will belong to the RMH and will be retained and stored securely with the Royal Marsden NHS Foundation Trust for a period of 5 years.

Any communication arising from this research that enters the public domain, including publications, press releases, websites, presentations, posters and participant materials **correctly acknowledge the NIHR and use the new NIHR identity and will acknowledge support from the BRC.**

Publication: "Any activity that discloses, outside of the circle of trial investigators, any final or interim data or results of the study or any details of the study methodology that have not been made public by the Sponsor including, for example, presentations at symposia, national or regional professional meetings, publications in journals, theses or dissertations."

All scientific contributors to the study have a responsibility to ensure that results of scientific interest arising from Trial are appropriately published and disseminated. The Sponsor has a firm commitment to publish the results of the Trial in a transparent and unbiased manner without consideration for commercial objectives.

To maximise the impact and scientific validity of the study, data shall be consolidated over the duration of the trial, reviewed internally among all investigators and not be submitted for publication prematurely.

## 19. Abbreviations

---

Acronym	Meaning
CCR	Committee for clinical research
CI	Chief investigator
CRF	Case report form
GCP	Good clinical practice
HNC	Head and neck cancer
HPV	Human papilloma virus
IRAS	Integrated research application system
ISF	Investigator site file
MDADI	M. D. Anderson Dysphagia Inventory
MDT	Multidisciplinary team
OPC	Oropharyngeal cancer
PI	Principal investigator
PPI	Patient and public involvement
PIN	Patient identification number
PSS-HN	Performance status scale for head and neck cancer
QoL	Quality of life
R&D	Research and development
REC	Research ethics committee
RM	Royal Marsden
SLT	Speech & Language Therapist/Therapy
SOP	Standard operating procedure
UWQoL4	University of Washington Quality of Life Questionnaire
WST	Water swallow test

## Appendix 1: Performance Status Scale in Head and Neck cancer standard operating procedure (SOP)

---

### Purpose:

To describe the procedures employed when evaluating the Normalcy of Diet, Place of Eating and Understandability of Speech scores using the Performance Status Scale for Head and Neck Cancer (PSS-HN).

### Scope:

This SOP outlines the procedure to be carried out by the co investigator or trained Speech and Language Therapists (SLTs), performing the PSS-HN.

### Procedure:

#### Timing of assessments

The PSS-HN assessment is to be carried out at the time points as specified in the protocol: at baseline, and at 3, 6, and 12 following diagnosis. The PSS-HN assessment is to be carried out after completion of the patient reported outcomes, to avoid bias on self-reporting, but before the instrumental FEES assessment.

#### Assessor

The PSS-HN assessment should only be performed by appropriately trained staff including a member of the research team or trained SLT.

#### Assessment

It is anticipated that the PSS-HN assessment will take approx. 5 minutes to complete.

Scores for the PSS-HN assessment are determined following an unstructured interview. The scores range from 0 to 100, with higher scores indicating better performance. There are separate scores for each of the 3 subscales. The subscales with the various food items and options can be found in the associated guidance document.

Interviewer instructions for the three subscales are outlined below.

#### Normalcy of diet

It is recommended that the assessor begins by asking the patient what kinds of food they have been eating, and what foods have been difficult to eat. Based on the patient's response, an item should be chosen at the low end of the scale.

The assessor should move up the scale giving examples of foods in each category, asking the patient whether they are eating these foods. Even if a patient states they eat everything, enquiries should be made about specific items beginning with score 50 (soft chewable foods) and move upwards.

The assessor should stop at an item at, and above, which the patient cannot eat. The patient receives the score below this item.

If the patient eats a full diet, an enquiry should be made if the patient needs to drink more liquids than usual with meals. Eating a full diet with intake of extra fluids is scored 90.

If the patient can take foods orally, but is also using a feeding tube, the score should be based on solid foods and indicate that a feeding tube is used.

### Public eating

The patient should be asked:

- where they eat – in a restaurant, at home, at friends/relatives' homes, etc.
- with whom they eat – always alone, with family/friends, etc.
- if they choose different foods when eating with others – softer, less messy, etc.
- when was the last time they ate in a restaurant, MacDonald's, picnic, family reunion.

The score beside the description that best fits the patient should be chosen. A patient on a restricted diet (e.g. tube feeding, pureed foods) who does not eat in public but will join others in a public eating setting should be scored 75. Inpatients should receive a score of 999.

### Understandability of speech

This score is based on the interviewer's ability to understand the patient during conversation (in this case, based on conversation about normalcy of diet and public eating). The score beside the description that best fits the patient should be chosen. The assessor should assess the clarity of speech when not directly facing the patient, or whether face-to-face contact is required to understand them.

Normalcy of Diet	Eating in public	Speech intelligibility
100 Full diet with no restrictions	100 No restriction of place, food or companion (eats out at any opportunity)	100 Always understandable
90 Full diet with liquid assistance	75 No restriction of place, but restricts diet when in public (eats anywhere, but may limit intake to less "messy" foods (e.g., liquids)	75 Understandable most of the time; occasional repetition necessary
80 All meats	50 Eats only in presence of selected persons in selected places	50 Usually understandable; face-to-face
70 Carrots, celery (crunchy)	25 Eats only at home in presence of selected persons	25 Never understandable; may use written
60 Dry bread & crackers	0 Always eats alone	0 No communication
50 Soft, chewable foods (pasta, canned soft fruits, fish)		
40 Soft foods requiring no chewing e.g. mashed potato, apple sauce		
30 Puree		
20 Warm liquids		
10 Cold liquids		
0 Non oral		

### CRF completion

The PSS-HN assessment CRF should be completed as soon as possible after completion of the assessment.

## Appendix 2: IDDSI Functional Diet Score: SOP

---

### Purpose:

To describe the procedures employed when evaluating the IDDSI functional diet score

### Scope:

This SOP outlines the procedure to be carried out by the co investigator or trained Speech and Language Therapists (SLTs), when assigning the IDDSI functional diet score.

### Procedure:

#### Timing of assessments

The IDDSI functional diet score is to be carried out at the time points as specified in the protocol: at baseline, and at 3, 6, and 12 following diagnosis.

### Assessor

The IDDSI functional diet score assessment should only be performed by appropriately trained staff a member of the research team or trained SLT.

### Assessment

It is anticipated that the IDDSI functional diet assessment will take approx. 2 minutes to complete. Scores for the IDDSI functional score are determined following an unstructured interview regarding the food and drinks currently being managed by the patient. The scores range from 0 to 8 with higher scores indicating better function.

The IDDSI Functional Diet Scale score corresponds to the number in the intersecting cell of the column showing the food level and the row showing the drink level recommended for the patient. An IDDSI Functional Diet Scale score of 0 applies for recommendations of nothing by mouth (NPO), with exclusive nonoral feeding.

FOOD LEVELS							N/A (no drinks)	DRINK LEVELS
7	6	5	4	3	N/A (no food)			
3	2	1	N/A	N/A	0	N/A (no drinks)		
4	3	2	1	N/A	N/A		4	
5	4	3	2	1	N/A		3	
6	5	4	3	2	1		2	
7	6	5	4	3	2		1	
8	7	6	5	4	3		0	

## Appendix 3: 100ml Water Swallow Test (100ml WST) SOP

---

### Purpose:

To describe the procedures employed when evaluating swallowing using the 100ml WST.

### Scope:

This SOP outlines the procedure to be carried out by the co investigator or trained Speech and Language Therapists (SLTs), performing the 100ml WST.

### Procedure:

#### Timing of assessments

The 100ml WST is to be carried out at the time points as specified in the protocol: at baseline, and at 3, 6, and 12 following diagnosis.

#### Assessor

The 100ml WST should only be performed by a member of the research team or trained SLT

#### Assessment

It is anticipated that the 100ml WST assessment will take approx. 2 minutes to complete.

Patient should be alert, in an upright, comfortable position. If possible, the patient should be allowed to rest for a few minutes after arrival to gain composure.

If a patient is already using a head posture on fluids to eliminate aspiration/ penetration the WST should still be performed. This does not mean an immediate fail.

If patients are anxious about doing the test, a tester cup can be given to patients to reduce anxiety prior to the actual test. The tester cup can also be used to help patients clear any secretions from the throat before the WST is performed.

Whether a tester cup is appropriate is left to the clinical judgement of the treating SLT or the individual delegated to perform the WST.

It should also be re-emphasised that patients can take as much time as they need and they may stop the test at any time if they feel uncomfortable

The following is needed to perform the WST:

- Stopwatch
- Plastic cup
- Syringe or measuring cup
- Tap water

#### Face-to-face assessment:

The assessor measures 100mL of water (neither warm, nor chilled) in a plastic cup using the syringe or measuring cup.

The patient is asked to drink all the water “as quickly as possible, without making themselves uncomfortable”, and without trying to talk during the assessment.

The assessor simultaneously places their fingers gently on the patient's thyroid cartilage to measure the number of swallows. Timing starts when the water touches the patient's bottom lip and stops on the last swallow (including any breaks that might be required between swallows), including any final clearance swallow.

The WST should not be performed if individuals have been recommended by their managing clinician to remain nil by mouth.

If there are overt signs of significant aspiration (explosive coughing, prolonged coughing) or the patient is becoming distressed, the assessment and timing is stopped immediately and the remaining amount of water measured and recorded.

It is acceptable if patients cannot finish the test – inability to complete the test is an important result and should be reported on the CRF by recording how much water the patient swallowed.

It is recommended that patients who are unable to complete the WST should be highlighted to SLTs for further review as per standard care.

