### Secondary endpoints

1. MDADI composite score at baseline and 3 and 6, months following surgical or re-irradiation treatment or 3 and 6, months into non-surgical treatment.
2. Mean PSS-HN Normalcy of diet, public eating and speech intelligibility using the PSS-HN scale scores at 3 and 6 months .
3. Median (IQR) IDDSI functional diet score International dysphagia diet standardisation initiative functional diet scale (IDDSI-FDS) at baseline and 3 and 6 months following surgical or re-irradiation treatment or 3 ad 6,months into non-surgical treatment.
4. Mean 100ml WST capacity score score at baseline and 3 and 6, months following surgical or re-irradiation treatment or 3 and 6 months into non-surgical treatment.
5. FEES DIGEST summary score at baseline and 3 and 6 months following surgical or re-irradiation treatment or 3 and 6months into non-surgical treatment.
6. Mean UW-QoL4 composite physical, social and functional scores at baseline and 3 and 6 months following surgical or re-irradiation treatment or 3 and 6 months into non-surgical treatment.
7. Number and percentage of patients ranking of CPS categories (1-12) in order of importance, at baseline and 6 months following surgical or re-irradiation treatment or 6 months into non-surgical treatment
8. Number and percentage of patients still alive at the end of the study
9. Number and percentage of patients using a gastrostomy at each time point at baseline and 3 and 6 months following surgical or re-irradiation treatment or 3 and 6 months into non-surgical treatment.

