### Part A

Part A: The sample size calculation is based on the primary endpoint, change in MDADI scores from baseline and 6 months following diagnosis/treatment of recurrent disease. Previous data has shown that a 10-point between-group difference in MDADI score is clinically significant (Hutcheson et al 2016). This end point has not been measured systematically previously in recurrent disease patients.

Pilot data collected at the Royal Marsden Hospital available for a service evaluation was used to look MDADI score in this cohort of patients. Data based on 10 patients shows a mean composite score of 66.50 at baseline and 52.60 at 6 months with a standard deviation of the difference of 23.68.

With a two-sided alpha of 5% and 95% power a total of 40 participants will be required to complete the paired questionnaires at baseline and 6 months post-treatment (power function, STATA). An additional 4 patients will be recruited to cover for 10% drop out for a total sample of 44 patients. Seventy-five patients are referred to the Royal Marsden Hospital per year with recurrent OPC and this number is set to increase with the on-going developments in robotic surgery, experimental trials and the development of the International Centre for Recurrent Head and Neck Cancer (IReC). Data collection will take place over an 18-month period.

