### Part A

Baseline patient characteristics (age, gender, ethnicity and previous HNC treatment history) will be summarized in addition to the diagnostic and treatment details (site of recurrence, type of treatment, use of reconstruction, tracheostomy, feeding tube presence/ type) using descriptive statistics.

The primary endpoint data will be analysed to compare the mean change from baseline MDADI composite score to 6 months into or post treatment using a two-sided paired t-test if data are normally distributed. In the event of not normally distributed data non-parametric-methods (Wilcoxon Signed Rank test) will be used.

Secondary endpoints (PSS, 100ml WST, IDDSI functional diet score, FEES-DIGEST and UW-QOL, and CPS scores) will be summarised using summary statistics (mean with standard deviation if data are normally distributed or median with IQR if data have a skewed distribution). Counts and percentages will be presented with 95% confidence intervals.

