#### Recording and Reporting

The assessor records:

- The number of swallows taken
- The time taken to complete the task (in seconds; round to nearest second)
- The amount of water the patient swallowed
- The presence/absence of any signs of aspiration/ penetration (throat clear/ cough/ wet voice) during or after the task.

In the database input swallow volume (mls swallowed / number of swallows) swallow capacity (mls swallowed / time taken in seconds)

CRF completion

The 100ml WST assessment CRF should be completed as soon as possible after completion of the assessment.

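### The 100 ml water test summary leaves out nil-by-mouth patients without scoring or counting them, so it can understate a decline in swallowing

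*Combined protocol and SAP*

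**What the plan says.** **Who is tested.** Appendix 3, face-to-face assessment: "The WST should not be performed if individuals have been recommended by their managing clinician to remain nil by mouth". The remote assessment instructions in the same appendix do not repeat this bar. A patient who starts but cannot finish is kept: "inability to complete the test is an important result and should be reported on the CRF by recording how much water the patient swallowed".

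**What is computed.** Appendix 3, recording and reporting, defines "swallow capacity (mls swallowed / time taken in seconds").

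**What is reported.** Secondary endpoint 4 in section 6 is the "Mean 100ml WST capacity score" at baseline, 3 and 6 months. Section 11, Part A, plans summary statistics for the secondary endpoints: "mean with standard deviation if data are normally distributed or median with IQR if data have a skewed distribution". It has no rule for a patient who was not tested.

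**How the same state is handled elsewhere.** The Normalcy of Diet scale in Appendix 1 gives 0 to a patient with no oral intake. In Appendix 2, "An IDDSI Functional Diet Scale score of 0 applies for recommendations of nothing by mouth (NPO), with exclusive nonoral feeding", and "The scores range from 0 to 8 with higher scores indicating better function". Table 4 in section 9, however, lists the diet score as running from 1 to 8.

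**The concern.** Secondary objective 1 in section 5 is to investigate changes in function up to 6 months, and water test capacity is one of the measures named for it. A patient who becomes nil by mouth during follow-up has usually had an important loss of swallowing function. On the two diet scales that patient moves to the floor. On the water test the patient leaves the summary.

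Whether capacity is missing thus depends on the thing being measured. A tested-only mean or median at 6 months describes a selected group, and nothing in the plan tells the reader how many patients were left out for this reason. The capacity figure could look stable or better while swallowing in the cohort got worse, and could then disagree with the Normalcy of Diet mean, which keeps these patients at 0.

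**Working it through.** **The plan's own figures.** The documents give no expected value or sample size for endpoint 4, so there is nothing to reproduce for it. The only stated calculation, for the MDADI primary endpoint, does reproduce: the pilot "mean composite score of 66.50 at baseline and 52.60 at 6 months" gives a difference of 66.50 - 52.60 = 13.90. With a standard deviation of the difference of 23.68 and two-sided alpha of 5%, a paired t-test with 40 pairs has power 0.952. It does not depend on the water test.

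**Step 1: does the plan assign a value?**

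| Patient's state | Water test capacity | Normalcy of Diet | IDDSI diet score |
|---|---|---|---|
| Starts, cannot finish | ml swallowed / seconds | scored by diet | scored by diet |
| Nil by mouth | not performed; no value | 0 | 0 |

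With no test there is neither a volume nor a time, so the formula gives nothing. Section 11 chooses between mean and median by the shape of the data. Both then cover tested patients only.

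**Step 2: size against a zero convention.** Let p be the share of patients seen at a visit who are nil by mouth (not in the documents; assumed) and m the tested-only mean. If nil by mouth counts as 0 ml/s, the mean over all patients seen is (1-p)m. The tested-only mean is too high by m/[(1-p)m] - 1 = p/(1-p), whatever the distribution.

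| Assumed p | p/(1-p) | Tested-only median as a percentile of all seen, 50 + 50p |
|---|---|---|
| 5% | 0.05/0.95 = 5.3% | 52.5th |
| 10% | 0.10/0.90 = 11.1% | 55th |
| 20% | 0.20/0.80 = 25.0% | 60th |

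The last column needs only that nil-by-mouth patients rank below tested ones.

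**Step 3: what this does to change.** Under the same convention, the ratio of the 6-month to the baseline mean over all patients is the tested-only ratio multiplied by (1-p6)/(1-p0), where p0 and p6 are the shares at the two visits. Equal shares cancel. If nobody is nil by mouth at baseline and 10% are at 6 months, the factor is 0.90, and the tested-only figures omit it. If the share falls over time, the tested-only figures understate recovery instead.

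**Step 4: can the mean hold or rise while function falls?** Two illustrations, both with assumed capacities.

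- Baseline evenly spread over 1 to 15 ml/s (mean 8.0), nobody else changes. If the lowest 10% become nil by mouth, the cut is 1 + 14 x 0.10 = 2.4. The tested-only mean is (2.4 + 15)/2 = 8.70 and the all-patient mean is 0.9 x 8.70 = 7.83. If a random 10% do, the tested-only mean stays at 8.0 on average and the all-patient mean is 7.2.
- Forty patients evenly spaced from 2 to 18 ml/s (mean 10.0). The lowest become nil by mouth and everyone still tested loses 0.5 or 1.0 ml/s:

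| Nil by mouth | Loss, ml/s | Tested-only mean | Mean with nil by mouth = 0 |
|---|---|---|---|
| 5% | 0.5 | 9.91 | 9.41 |
| 10% | 0.5 | 10.32 | 9.29 |
| 10% | 1.0 | 9.82 | 8.84 |
| 15% | 1.0 | 10.23 | 8.70 |
| 20% | 1.0 | 10.64 | 8.51 |

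So the mean can rise, but in this example only from about 10% nil by mouth with a 0.5 ml/s loss, or about 15% with a 1.0 ml/s loss. Below that it falls by less than the zero-scored mean. Restricting to patients tested at both visits removes the false rise (at 10% and 0.5 ml/s the paired change is -0.5) but still omits those who got worst. The zero-scored mean falls by 10.0 - 9.29 = 0.71.

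**Step 5: is the direction fixed?** No. With capacities 4, 8 and 12 (mean 8), losing the patient at 12 lowers the tested-only mean to (4 + 8)/2 = 6. The zero-scored mean falls further, to (4 + 8 + 0)/3 = 4.

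**The case against.** The strongest reply is that nil-by-mouth status is not lost. The IDDSI score is 0 for exactly this state, is taken at the same visits and can be collected remotely. Normalcy of Diet is also 0, and gastrostomy use is counted at each visit. The number untested for this reason can largely be derived. This stands, and it is why the point is small. It does not repair the capacity summary: endpoints 2 and 3 report a mean and a median, not the number at 0, and a feeding tube is not the same as nil by mouth, since Appendix 1 provides for patients who eat while using one.

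Second, the water test CRF is not among the documents and may already have a field for a test not done. That also stands. The list in Appendix 3 shows what is recorded when the test takes place and cannot show what the form lacks.

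Third, zero is natural for a diet scale whose lowest category is no oral intake, but capacity is a measured flow rate. A patient held nil by mouth for aspiration risk may have some. Zero is therefore a convention, and so are the percentages built on it.

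Fourth, a reader might infer that every patient who becomes nil by mouth pushes the reported mean up or leaves it unchanged. Step 5 shows that this is false. Nor does the pilot MDADI fall of 13.9 points show that nil by mouth will be common: it is a questionnaire result in 10 patients. A reader might also infer from Table 4 that these patients drop out of endpoint 3. Section 9 refers to the Appendix 2 procedure, which includes 0, so Table 4 is better read as a labelling inconsistency.

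**Conclusion.** The gap is real and modest. The plan rightly withholds the test from nil-by-mouth patients, but gives them no capacity value and does not ask for their number to be reported. Endpoint 4 therefore summarises tested patients only, with missingness that depends on swallowing function. The tested-only mean can understate decline, and can hold or rise while function falls if those lost are mostly poor swallowers.

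The documents do not support saying that it will rise. They contain neither the nil-by-mouth share nor the capacity distribution. The 5.3%, 11.1% and 25% rest on assumed shares of 5%, 10% and 20% and on the 0 ml/s convention, and they apply to the level at one visit. The distortion of change depends on how the share differs between visits.

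Endpoint 4 is one of nine secondary endpoints in an exploratory study, with no test planned on it. The primary endpoint is unaffected. This is a cheap improvement to the reporting of one measure and does not threaten the study's main result.

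**What to change.** - **Count.** At baseline, 3 and 6 months, report the number tested and the number not tested because nil by mouth. Record the reason on the water test CRF if it is not already there, or derive it from an IDDSI score of 0.
- **Summarise.** In section 11, keep the stated mean but label it as covering tested patients only. Beside it give the median capacity with nil by mouth ranked lowest. Summarise change under the same rule in patients seen at both visits, so that a move to nil by mouth counts as a decline and a return to oral intake as a gain.
- **Extend the safety bar.** Move the nil-by-mouth rule from the face-to-face instructions to the general assessment text of Appendix 3, so that it also covers remote testing.
- **Correct Table 4.** Change the diet score range to 0-8 to match Appendix 2.

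The cost is one moved sentence, at most one CRF item, one analysis sentence and one table entry, with no extra visits or patients. The downside is that ranking nil by mouth lowest is a convention, since some patients held nil by mouth for aspiration risk may have measurable capacity. The median needs only the ranking, not the value 0, and the tested-only mean stays in view.
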